7.2.2 Sub-study background and rationale

Colorectal cancer is the fourth most common cancer type in the UK with over 40, 000 cases diagnosed annually (CRUK, 2015).

While features such as advanced disease stage at presentation can be used to identify patients at risk of poor long-term outcomes, a number of more subtle markers exist which can predict adverse outcome in both the short- and long-term. Body composition techniques assess the distribution of adipose tissue relative to lean muscle mass on CT and can be used to predict post-operative complications and survival in patients undergoing colorectal cancer resection. Depleted skeletal muscle mass, also known as myopenia, confers an unfavourable prognosis, with negative effects on short-term surgical outcomes including higher rates of infective complications (Huang et al., 2015, Joglekar et al., 2015) and prolonged length of stay (Joglekar et al., 2015, Reisinger et al., 2015) as well as poorer long-term survival (Malietzis et al., 2016a, Feliciano et al., 2017). A recent meta-analysis examining the prognostic role of myopenia in patients undergoing gastrointestinal cancer resection reported a prevalence of between 12 to 60% in colorectal populations (Simonsen et al., 2018). The underlying aetiology is multifactorial and poorly understood but includes systemic inflammation, endocrine imbalance and negative energy balance, with impairment manifesting as loss of function and fatigue (Pring et al. 2018). Myopenia can be readily measured on pre-operative CT imaging, providing a quantifiable measure of those at risk of poor outcome following colorectal cancer resection.

The systemic inflammatory response (SIR) represents a further established indicator of adverse post-operative outcome. The presence of an elevated SIR prior to elective colorectal cancer resection is associated with higher rates of infective complications (Moyes et al., 2009) and poorer cancer-specific survival (Crozier et al., 2007), independent of comorbidity (Roxburgh et al., 2011). Its association with myopenia has been explored in colorectal cancer populations previously: Richards and colleagues reported a relationship between elevated SIR markers and reduced skeletal muscle index (Richards et al., 2012), while Malietzis found patients with an elevated neutrophil: lymphocyte ratio (NLR) had significantly lower skeletal muscle mass when compared with their non-inflamed counterparts (Malietzis et al., 2016b). More recently, Feliciano and co-workers confirmed a dose-response relationship between the NLR and degree of myopenia, which translated to reduced overall and cancer-specific survival (Feliciano et al., 2017).

The independent prognostic value of metrics derived from muscle and fat CT analysis and the inflammatory response presents a context in which to risk-stratify patients pre-operatively. Patients who are identified as high risk for adverse outcome through these features may require more intensive or targeted interventions to address their adverse risk profile. In healthy subjects, exercise by repetitive muscle use physiologically leads to an increase in muscle mass and also imparts anti-inflammatory effects by attenuating the cellular response to pro-inflammatory cytokines whilst

increasing circulating levels of anti-inflammatory cytokines (Keller et al., 2004, Starkie et al., 2003, Gould et al., 2013, Steensburg et al., 2002, Petersen and Pedersen, 2005, Steensburg et al., 2003).

While several studies have explored prehabilitation in patients with cancer with the aim of improving fitness, the effect of exercise on preservation of lean muscle mass or attenuation of muscle wasting has not yet been examined (Bruns et al., 2016). Similarly, the influence of SIR status on response to prehabilitation as measured by change in cardiorespiratory fitness remains unexplored. By assessing the presence and degree of myopenia on the staging and first surveillance CT scans in the 12 months following surgery carried out as part of standard care in patients participating in the PREPARE-ABC trial, it may be possible to address whether prehabilitation can be used to improve muscle quality and prevent muscle wasting in response to the acute insult of surgery. Furthermore, combining assessment of myopenia with the pre-operative systemic inflammatory response may enable patients to be risk-stratified in order to interpret their subsequent response to prehabilitation.

7.2.3 Sub-study objectives

As in the main study, there will be three trial arms:

- Arm A Hospital based supervised exercise
- Arm B Home based supported exercise
- Arm C Standard care, treatment as usual

There are two primary research hypotheses:

- hospital-supervised exercise training in the pre- and post-operative period, in addition to standard care, leads to a change in muscle attenuation at 12 months versus standard care alone.
- home-supported exercise training in the pre- and post-operative period, in addition to standard care, leads to a change in muscle attenuation at 12 months versus standard care alone.

An exploratory hypothesis that hospital-supervised exercise training in the pre- and post-operative period, in addition to standard care, leads to a change in muscle attenuation at 12 months versus home-supported exercise will also be examined.

7.2.3.1 Sub-study primary objectives

 To assess the effect of a formal pre- and post-operative exercise programme on muscle and visceral adiposity (including the reversal/arrest of myopenia) and the systemic inflammatory response in the PREPARE-ABC trial.

7.2.3.2 Sub-study secondary objectives

- To assess the dose-response associations between the amount and type of exercise that is undertaken by participants in the PREPARE-ABC trial and preservation of skeletal muscle on CT in the PREPARE-ABC trial
- To examine the association between myopenia at baseline and subsequent change in preoperative cardiopulmonary fitness variables in participants in the PREPARE-ABC trial
- To examine the association between systemic inflammation at baseline and subsequent change in pre-operative cardiopulmonary fitness variables in participants in the PREPARE-ABC trial

- To assess the effect of myopenia and/or systemic inflammation at baseline on complications in the post-operative period in the PREPARE-ABC trial
- To determine the relationship between the presence of myopenia on CT and grip strength in the PREPARE-ABC trial

7.2.4 Methods

7.2.4.1 Sub-study participant eligibility criteria

In addition to the eligibility criteria for participation in the PREPARE-ABC study, patients will be eligible for inclusion in the sub-study if:

- a pre-operative staging CT scan suitable for body composition (muscle and fat) analysis within the 6 months preceding enrolment in PREPARE-ABC is available
- height and weight were recorded at baseline
- results are available for full blood count and liver function tests (with or without CRP) taken within the 3 months preceding enrolment in the main trial

7.2.4.2 Sub-study consent procedures

We shall be collecting fully anonymised routine clinical data as part of this study. In accordance with section 4 of the existing consent form and in view of the fact that no further intervention or investigation of patients is required no further specific consent shall be sort for this sub-study analysis.

Inclusion in the sub-study will be independent of adherence to treatment arm within the main study. Patients who discontinue the main trial treatment but remain in the trial for follow-up will be included in data analysis of both the main trial and sub-study (where applicable).

Withdrawal from the main trial includes a withdrawal from the sub-study. Data already collected will be kept and included in sub-study analyses for all participants who stop follow up early.

7.2.4.3 Outcomes

7.2.4.3.1 Primary Outcomes

Outcome: Change in muscle mass

Change in muscle mass will be assessed using image analysis of the pre-operative and first surveillance CT scans obtained as part of routine care for standard care versus hospital-based and standard care versus home-based intervention groups.

7.2.4.3.2 Secondary Outcomes

The following secondary outcomes will be assessed for standard care versus hospital-based and standard care versus home-based exercise interventions:

Outcome: Change in systemic inflammatory response

Change in systemic inflammatory response will be assessed using the neutrophil:lymphocyte ratio (NLR) and modified Glasgow Prognostic Score (mGPS) measured on serum blood tests obtained as part of routine care (at diagnosis and prior to surgery).

Outcome: Pre-operative change in cardiopulmonary fitness

Change in cardiopulmonary fitness will be measured using CPET variables, as measured using an incremental CPET between 4 weeks prior to surgery and shortly before surgery obtained as part of the main trial. Variables assessed will include but not be limited to peak VO₂, anaerobic/ventilatory threshold, VE/VCO₂ and oxygen pulse.

Outcome: Pre-operative change in grip strength

Metric: Change in grip strength as measured using a standard digital grip strength dynamometer.

7.2.4.3.3 Sample size

The primary outcome is the change in mean muscle attenuation on CT at 6 months. For a comparison between two groups (standard care versus hospital-based and standard care versus home-based exercise interventions), a total of 95 participants per group (285 in total) will be required. This will have 90% power to detect a difference of 5 HU in mean muscle attenuation between any two treatment groups, assuming a standard deviation of 9.4 HU and a significance level of 5%, using a t-test. This will account for a drop-out rate of 20%.

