5.9.1.1 Sequence generation

Eligible, consented participants will be randomised on a 1:1:1 basis to one of three trial arms using a web based randomisation process. The randomisation scheme will be generated by the NCTU data manager and notified by email to the study team. Allocation will be stratified by centre using permuted block randomisation with randomly varying block sizes.

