7.2.7 Sub-study statistical methods

Statistical analysis will be performed using SPSS software (Version 24.0. SPSS Inc., Chicago, IL, USA).

Descriptive statistics will be used to analyse the baseline characteristics of the study population. For the primary outcome of muscle attenuation at 6-12 months post-procedure, the two groups (standard

care versus hospital-based and standard care versus home-based exercise interventions) will be compared using chi-squared test. Similar methods will be used to assess the change in muscle mass between each group, from baseline to their post-operative CT. Previous research (Martin et al) has suggested a standard deviation for this outcome of 9.4 HU. A difference in outcome between groups of 5 HU would be regarded as clinically important.

Dose Response Relationships

Using the self-reported physical activity data recorded in the patient exercise diaries, the sub-study team will correlate type and amount of exercise against changes in muscle mass. The muscle mass will be calculated as described above making particular note of mean muscle attenuation and L3 muscle area.

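### Sub-study: adjusting the muscle-attenuation comparison for baseline attenuation and centre is a free gain in precision that the stated unadjusted two-group tests leave unused

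*Protocol*

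**What the plan says.** **Sizing.** Protocol 7.2.4.3.3 takes as primary outcome the change in mean muscle attenuation on CT at 6 months. It says that "a total of 95 participants per group (285 in total) will be required", that "This will have 90% power to detect a difference of 5 HU in mean muscle attenuation between any two treatment groups", and it does so "assuming a standard deviation of 9.4 HU and a significance level of 5%, using a t-test". The number includes an allowance for 20% drop-out. No covariate is mentioned.

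**Analysis.** Protocol 7.2.7 describes the primary outcome as muscle attenuation at 6 to 12 months after the procedure, and compares each exercise arm with standard care by a chi-squared test. Change in muscle mass from baseline is to be handled by similar methods. Again no covariate is named. This section also says that earlier research "has suggested a standard deviation for this outcome of 9.4 HU", without saying whether that outcome is a single value or a change.

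**Baseline.** Protocol 7.2.4.1 admits a patient to the sub-study only if "a pre-operative staging CT scan suitable for body composition (muscle and fat) analysis within the 6 months preceding enrolment in PREPARE-ABC is available".

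**Centre.** Protocol 5.9.1.1: "Allocation will be stratified by centre using permuted block randomisation with randomly varying block sizes". For continuous outcomes of the main trial, 5.10.4.6 uses a general linear model with site in it and gives the stratification as the reason.

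**Deferral.** Protocol 7.2.7.2 announces a separate sub-study SAP covering the statistical aspects. It is not among the documents.

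**The concern.** The sub-study uses the main trial's randomisation, yet both of its stated comparisons leave out the stratification factor for which the main trial adjusts. They also leave out, as a covariate, the one measurement likely to explain most of the variation in the outcome. That measurement is already in hand for every participant.

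How far baseline is used depends on which section is followed. Under 7.2.4.3.3 the outcome is a change, so baseline enters by subtraction. Under 7.2.7 the outcome is the follow-up value, and baseline plays no part. Subtraction is a fixed adjustment with slope 1. It matches regression adjustment only when the true slope is 1, and it adds noise when the correlation between the two scans is below 0.5.

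What is at stake is precision in a small sub-study of 95 per arm, or 76 after drop-out. There is also a robustness question. If 9.4 HU describes a single scan and raw change is then compared, the stated 90% power may not be reached.

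**Working it through.** **Inputs from the protocol (7.2.4.3.3).** Difference 5 HU; SD 9.4 HU; significance level 5% (sidedness not stated; two-sided taken, because it reproduces the stated number); power 90%; drop-out 20%; 95 per group.

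**Inputs not in the protocol.** The correlation r between baseline and follow-up attenuation, shown over a range; equal SD at the two scans; a centre intraclass correlation of 0.01 to 0.05. The one or few degrees of freedom spent on covariates are ignored.

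**1. Reproduce the stated figure.**
- Normal approximation: n = 2 × (1.960 + 1.282)² × 9.4² / 5² = 74.3, so 75 per group; 75 / 0.8 = 93.75, so 94.
- Exact two-sample t-test: n = 75.2, so 76 per group; 76 / 0.8 = 95. This is the protocol's number.
- Exact power at 76 per group: 90.3%.

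The sizing sentence is correct if 9.4 HU is the SD of whatever is analysed.

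**2. Residual SD after baseline adjustment.**
- If 9.4 is the SD of a single value: 9.4 × √(1 − r²).
- If 9.4 is the SD of change: change has variance 2s²(1 − r) and the adjusted model has s²(1 − r²), where s is the single-time SD. The ratio is (1 + r)/2, so the residual SD is 9.4 × √((1 + r)/2).

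**3. Power of the adjusted comparison (76 per arm, 5 HU, two-sided 5%, noncentral t), against 90.3%.**

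| r | 9.4 = single-time SD | 9.4 = SD of change |
|---|---|---|
| 0.3 | SD 8.97, 92.7% (+2.4) | SD 7.58, 98.1% (+7.8) |
| 0.5 | SD 8.14, 96.4% (+6.1) | SD 8.14, 96.4% (+6.1) |
| 0.7 | SD 6.71, 99.5% (+9.2) | SD 8.67, 94.2% (+3.9) |
| 0.9 | above 99.9% | SD 9.16, 91.7% (+1.4) |

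In the single-time column the comparator of 90.3% is the unadjusted follow-up value; in the other column it is the unadjusted change.

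**4. The exposed case: 9.4 is a single-time SD but raw change is compared.** The SD of change is then 9.4 × √(2(1 − r)).
- r = 0.3: SD 11.12, power 78.6%; adjusted 92.7%.
- r = 0.4: SD 10.30, power 84.5%; adjusted 94.5%.
- r = 0.5: SD 9.40, power 90.3%; adjusted 96.4%.

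Below r = 0.5 the unadjusted change comparison misses the stated 90%. The adjusted model does not.

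**5. Centre.** With centre removed from the residual, the SD is 9.4 × √(1 − ICC). At ICC 0.01 power is 90.6%, and at 0.05 it is 91.7%: a gain of about 0.3 to 1.4 points.

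**The case against.** The strongest reply has three parts.

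*The protocol's figure is right.* This stands. The 95 per group and the 90% power reproduce exactly under the stated t-test. A reader might infer that the sub-study loses power against its plan, or is under-sized. The documents do not support that in general: the target is met whenever 9.4 HU is the SD of the analysed outcome. A reader might also infer that the baseline scan is ignored altogether. That is not supported either, because Table 4, 7.2.4.3.1 and 7.2.4.3.3 all define the outcome as a change, so baseline enters by subtraction. What is absent is covariate adjustment.

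*The size is assumed.* This also stands. A gain of six points belongs to r = 0.5 alone, and the protocol gives no correlation. The staging scan may precede enrolment by up to 6 months and the follow-up scan is a routine one within 12 months of surgery, so no particular value can be defended. If 9.4 HU is the SD of change, the gain shrinks as r rises. The centre contribution is small, and leaving centre out tends to be conservative.

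*A t-test used for sizing does not fix the analysis, and the model belongs in the sub-study SAP.* This stands in part. Sizing on an unadjusted test and analysing with covariates is ordinary and conservative practice. But 7.2.7 is not silent. It names an unadjusted two-group test, and a SAP that followed it would inherit that choice. The chi-squared test is in any case unsuited to a continuous HU outcome, so the section needs rewriting. Replacing it only with the t-test of 7.2.4.3.3 would still leave the comparison unadjusted.

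**Conclusion.** The point holds as a free improvement, not as an error in the sample size. The stated comparisons adjust for neither baseline attenuation nor centre, although the first is available by design and the second is the stratification factor that the main trial's own model includes.

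The gain over 90.3% runs from about 2 to 9 points for r from 0.3 to 0.7 if 9.4 HU is a single-time SD, and from about 8 down to 1 point for r from 0.3 to 0.9 if it is the SD of change. Centre adds roughly 1 point at an assumed intraclass correlation of 0.05. All of these rest on correlations that the protocol does not give, and on equal variance at the two scans.

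The practical case is strongest where 9.4 HU is a single-time SD, raw change is compared and r is below 0.5. There the unadjusted comparison falls short of 90%, and the adjusted one keeps it. Since the protocol does not say which SD 9.4 HU is, this cannot be ruled out.

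**What to change.** In 7.2.7, replace the unadjusted test with a linear model of follow-up mean muscle attenuation (HU) on randomised arm, adjusted for baseline attenuation and for centre (as a random effect if centres are small). Report the adjusted mean difference with its 95% confidence interval for each exercise arm against standard care.

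In 7.2.4.3.3, keep 95 per group and state whether 9.4 HU is the SD of a single value or of change. If it is the SD of the outcome as analysed, the t-test calculation can be described as conservative for the adjusted model.

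The cost is a few lines in the sub-study methods and the same lines in its SAP. No new scans, data or patients are needed.

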7.2.5 Sub-study data collection

This sub-study does not require any visits or assessment outside of those required as part of standard care and/or participation in the PREPARE-ABC study.

The collaborating teams will be given access to the PREPARE-ABC database as appropriate; access will be managed by the NCTU trial and data management teams.

Each participant will be given a unique trial Participant IDentification Number (PID) following enrolment into PREPARE-ABC. This PID will be used to identify patients in the sub-study also. Data will be collected at the time-points indicated in the participant timeline.

All data will be handled in accordance with the Data Protection Act 1998 and GDPR (EU) 2016/679.

Basic demographic and clinicopathologic data is routinely collected as part of PREPARE-ABC. A number of these data will be required for sub-study analyses including but not limited to patient demographics, randomisation status, grip strength, CPET results, baseline height and weight and preand post-operative chemoradiotherapy details. In addition, for patients randomised to hospital-based or home-based exercise interventions, data from the supervised exercise sessions, motivational phone calls and exercise diary will also be included in the sub-study analyses.

Assessment of body composition

CT scans obtained as part of routine care at diagnosis and for cancer surveillance in the 12 months following surgery will be assessed for body composition analysis. DICOM images of the axial L3 vertebral level will be extracted by teams at each site. These data will be sent for analysis at St Mark's Hospital using SliceOmatic V5.0 software with the ABACS L3 Plug in.

The CT data will be analysed by automatic validated software which measures total fat, subcutaneous fat, visceral fat and skeletal muscle cross-sectional areas (cm^2) using standard Hounsfield unit ranges (adipose tissue: -190 to -30; skeletal muscle: -29 to +150, HU). Measurements will be standardised

for height to enable an index to be generated for each component, measured in cm²/m² (total fat index (TFI), subcutaneous fat index (SFI), visceral fat index (VFI) and skeletal muscle index (SMI)). Sexspecific cut-offs as defined by Prado and colleagues will be applied to the skeletal muscle index to categorise patients by presence of myopenia (SMI <52.4 cm²/m² for males and <38.5 cm²/m² for females).

Assessment of systemic inflammatory response

Serum blood samples obtained as part of routine care at the time of diagnosis and at the pre-surgery visit prior to surgery will be used to assess the systemic inflammatory response. This will include full blood count, liver function tests and, where available, C-reactive protein (CRP).

Baseline serum CRP (mg/L) and albumin (g/L) concentrations where available will be used to calculate the modified Glasgow Prognostic score as detailed in Table 1. Neutrophil: lymphocyte ratio will be calculated from the differential white cell count and values of greater than three considered as elevated. In patients who do not have a recorded pre-operative CRP, NLR alone will be used for assessment of SIR status.

[figure not shown]

Table 5: The modified Glasgow Prognostic Score

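### The sub-study words its myopenia objectives on a yes/no cut of the skeletal muscle index; the measured index, with sex in the model, would use more of the information at almost no cost (low priority)

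*Protocol*

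**What the plan says.** Section 7.2.5 measures skeletal muscle area on CT and standardises it for height, giving an index in cm²/m². Cut-offs of 52.4 for men and 38.5 for women are then "applied to the skeletal muscle index to categorise patients by presence of myopenia".

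Three of the secondary objectives in 7.2.3.2 use myopenia as the exposure. One is "To examine the association between myopenia at baseline and subsequent change in preoperative cardiopulmonary fitness variables". Another concerns the effect of baseline myopenia and/or systemic inflammation on post-operative complications. The third is "To determine the relationship between the presence of myopenia on CT and grip strength in the PREPARE-ABC trial".

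The background in 7.2.2 cites a meta-analysis that "reported a prevalence of between 12 to 60% in colorectal populations".

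For inflammation, 7.2.5 derives the NLR, with "values of greater than three considered as elevated", and also the modified Glasgow Prognostic Score (mGPS). Where CRP is missing, "NLR alone will be used for assessment of SIR status". The corresponding objective is "To examine the association between systemic inflammation at baseline and subsequent change in pre-operative cardiopulmonary fitness variables".

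Section 7.2.7 names no model for these objectives, and 7.2.7.2 promises a separate sub-study SAP.

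**The concern.** A yes/no split discards the differences among patients on the same side of the cut and treats patients just either side of it as fully different. If the relation with fitness, complications or grip strength is graded, the split version is more likely to miss it.

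This matters here because the sub-study was sized only for a 5 HU difference in muscle attenuation. The association objectives must work with whatever patients that yields, and the rationale in 7.2.2 wants to use such associations for risk stratification. The same section speaks of both the presence and the degree of myopenia, and cites an earlier study that "confirmed a dose-response relationship between the NLR and degree of myopenia". That study's question is not one of the sub-study's objectives, but it shows the authors think of myopenia as a matter of degree.

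**Working it through.** **The plan's own figure.** Section 7.2.4.3.3 gives 95 per group for 5 HU, SD 9.4, 90% power, 5% significance, a t-test and 20% drop-out. Taking 5% as two-sided, the normal approximation is 2 × (1.96 + 1.2816)² × (9.4/5)² = 74.3, so 75. The exact t-test needs 76, and 76/0.8 = 95. The stated figure reproduces and does not depend on the point made here.

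**Inputs for the check.**
- Prevalence of myopenia: 12–60% (7.2.2).
- Evaluable patients: 285 × 0.8 = 228. The 20% is stated for the primary CT outcome, so using it for these objectives is an assumption; 285 is also tried.
- Two-sided 5% test.
- Correlation r between SMI and a continuous outcome: not in the protocol, so assumed at 0.15 to 0.40.
- SMI normal within sex, association linear.

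**Information kept by a cut.** Splitting a normal exposure at prevalence p multiplies its correlation with the outcome by f = φ(z_p)/√(p(1−p)), and f² is the share of information kept.
- p = 12%: f = 0.616, f² = 0.379
- p = 30%: f = 0.759, f² = 0.576
- p = 50%: f = 0.798, f² = 0.637
- p = 60%: f = 0.789, f² = 0.622

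On this scale 228 patients with the cut do the work of about 228 × 0.379 = 86 at 12% prevalence, and 228 × 0.637 = 145 at best.

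**Power.** By Fisher's z, power ≈ Φ(atanh(r)·√(n−3) − 1.96). Worked example at n = 228 and r = 0.20: atanh(0.20) × 15 = 3.041, and Φ(3.041 − 1.96) = 0.860. With the cut at 12%, r becomes 0.123, atanh(0.123) × 15 = 1.856, and Φ(1.856 − 1.96) = 0.459.

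| r (assumed) | Measured SMI | Cut, 12% | Cut, 30% | Cut, 50% | Cut, 60% | Loss (points) |
|---|---|---|---|---|---|---|
| 0.15 | 62.1% | 28.4% | 40.3% | 43.8% | 43.0% | 18.3–33.6 |
| 0.20 | 86.0% | 45.9% | 63.1% | 67.5% | 66.5% | 18.5–40.1 |
| 0.25 | 96.9% | 64.3% | 82.1% | 85.8% | 85.0% | 11.1–32.6 |
| 0.30 | 99.6% | 80.0% | 93.5% | 95.6% | 95.1% | 4.1–19.6 |
| 0.40 | 100.0% | 96.5% | 99.7% | 99.9% | 99.8% | 0.1–3.5 |

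Simulation with 4,000 runs per setting, at r = 0.15 to 0.30 and prevalences of 12%, 30% and 50%, agreed to within about 2 points.

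With n = 285, the loss is 15–38 points at r = 0.20, 7–25 at 0.25 and 2–12 at 0.30.

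These figures apply to change in CPET variables and to grip strength. They do not apply to complications, which is a binary outcome.

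**The case against.** The strongest reply is that the analysis is not yet fixed. The cut-offs stand under data collection, the continuous index is derived before they are applied, and 7.2.7 uses measured attenuation and L3 muscle area for the exercise dose-response question. The detail is left to a sub-study SAP, and nothing forbids the measured index. It can also be said that myopenia is a diagnostic category, that the objectives ask about the category, and that no power is claimed for them.

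Much of this stands, and it is why the priority is low. It does not remove the point: the protocol states the categorisation and words its objectives on the category, so a SAP written from this text would naturally inherit the yes/no exposure.

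A reader might infer more than the text supports:
- **That the loss is large at any moderate correlation.** It is not. It is 4–20 points at r = 0.30 and 0–4 at r = 0.40, and the 40-point loss is one corner (r = 0.20, 12% prevalence, n = 228).
- **That NLR is likewise reduced to above or below 3.** Section 7.2.5 only labels values above three as elevated, 7.2.4.3.2 lists NLR as an outcome measure without a cut, and mGPS is used as well. No prevalence of NLR above 3 is given, so the figures above cannot be carried over.
- **That inflammation is to be related to grip strength, or that change in grip strength is the outcome for myopenia.** Section 7.2.3.2 states neither.
- **That 228 is the number for these objectives.** CPET change is measured before surgery and needs no surveillance CT, while CPET itself may be missing (5.6.1.3, 5.6.1.6). The true number is unknown.

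**Conclusion.** The point holds for SMI, as a cheap improvement of low priority. As worded, the protocol leads to a yes/no exposure that keeps roughly 38–64% of the information in the index over the prevalence range it cites. What that costs depends on a correlation the protocol does not give: it is substantial at 0.15–0.25, modest to moderate at 0.30 and negligible at 0.40. The size also rests on the assumed 228 patients, a normal exposure and a linear association, and it covers continuous outcomes only. The primary comparison and the 95 per group are untouched. For NLR, no loss can be shown from the text, and only a parallel recommendation is justified.

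**What to change.** In 7.2.5 and 7.2.7, and in the sub-study SAP, name continuous SMI as the main exposure for the myopenia objectives of 7.2.3.2, with sex in the model because the cut-offs differ by sex. Use linear regression for change in CPET variables and for grip strength, and logistic regression for complications. Keep myopenia yes/no as a secondary summary for comparison with published work.

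As a parallel step, analyse NLR on a continuous scale, for example its logarithm, alongside mGPS and the label for values above three.

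The cost is wording only, since the index and the ratio are already derived and no new data are needed. The small downside is that effects are expressed per unit and not as a yes/no contrast, which the retained summary covers.
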